6.7. ADDITIONAL ANALYSIS

6.7.1. ASES Comparison

The comparison of the ASES Shoulder Score must compare all Total ASES Shoulder Scores of all follow-up visits against each other (m x n) in accordance to table 6.7.1.1 and the analysis tables listed in this chapter. This analysis is part of the final report only.

Comparison		Follow-up Visits (n)											
		Preop	6 Weeks	6 Months	12 Months	24 Months	36 Months	48 Months	60 Months	72 Months	84 Months	96 Months	108 Months
Follow-up Visits B (m)	Preop												
	6 Weeks	x											
	6 Months	x	x										
	12 Months	x	x	x									
	24 Months	x	x	x	x								
	36 Months	x	x	x	x	x							
	48 Months	x	x	x	x	x	x						
	60 Months	x	x	x	x	x	x	x					
	72 Months	x	x	x	x	x	x	x	x				
	84 Months	x	x	x	x	x	x	x	x	x			
	96 Months	x	x	x	x	x	x	x	x	x	x		
	108 Months	x	x	x	x	x	x	x	x	x	x	x	
	120 Months	x	x	x	x	x	x	x	x	x	x	x	x

*All combinations marked with an "x" must be performed

Table 6.7.1.1: All Assessments – ASES Shoulder Score – Follow-up Visits to be compared

Evaluation Variable / Question	Level of Measurement	Analysis Plan
All Assessments – ASES Shoulder Score Comparison		
Use “ASES Total Score m [points]” and “ASES Total Score n [points]”: Based on the underlying distribution of the data in both groups and the result of the normality assessment, either the parametric paired samples t-test or the non-parametric Wilcoxon test will be used to compare “ASES Total Score m [points]” and “ASES Total Score n [points]” to evaluate the ASES Shoulder Score change by subject (improvement or decrease).		
The complete available SPSS tables content related to either the paired samples t-test or the Wilcoxon test will be included in the final report. (Variable(s): FINSCORE)		

Table 6.7.1.2: All Assessments – ASES Shoulder Score Comparison Tables List

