3.1. FRAMEWORK

All quantitative variables, including those based on calculations (secondary elements), will be analyzed with a case summary evaluation before the detailed characteristics and parameters can be evaluated. A case summary contains a listing of the number of valid cases/values, missing cases/values (if any) and total cases/values in the specific analysis. In general, a central position parameter for quantitative variables the mean, median and mode will be analyzed. As variation parameter the standard deviation, 95% confidence interval of the mean, interquartile range and range (based on maximum and minimum) will be calculated. All quantitative variables will be assessed for normality using the Shapiro-Wilk test. For optional visualization of quantitative variables, box-and-whisker plots will be used. Additional analyses like skewness and kurtosis measures or standard errors are optional also.

All qualitative variables, including those based on summaries (secondary elements), will be analyzed listing the proportions, frequencies, column and row totals, and missing proportion (if any).

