4.10. ASSUMPTIONS

In case of deviation from assumptions (e.g. normality), non-parametric methods will be used for analysis. No transformation of such data will be performed.

5. Population and Progress

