6.7.4. ASES Shoulder Score – Within subject changes by visit

The within subject score changes of the ASES Shoulder Score from visit to visit will be analyzed to help identifying the changes on the subject level. This analysis is part of the final report.

The within subject changes by visit of the ASES Shoulder Score must compare all follow-up visits against each other ($m \times n$) in accordance to table 6.7.4.1 and the analysis tables in this chapter.

Comparison		Follow-up Visits (n)												
		Preop	6 Weeks	6 Months	12 Months	24 Months	36 Months	48 Months	60 Months	72 Months	84 Months	96 Months	108 Months	120 Months
Follow-up Visits B (m)	Preop													
	6 Weeks	x												
	6 Months	x	x											
	12 Months	x	x	x										
	24 Months	x	x	x	x									
	36 Months	x	x	x	x	x								
	48 Months	x	x	x	x	x	x							
	60 Months	x	x	x	x	x	x	x						
	72 Months	x	x	x	x	x	x	x	x					
	84 Months	x	x	x	x	x	x	x	x	x				
	96 Months	x	x	x	x	x	x	x	x	x	x			
	108 Months	x	x	x	x	x	x	x	x	x	x	x		
	120 Months	x	x	x	x	x	x	x	x	x	x	x	x	

*All combinations marked with an "x" must be performed

Table 6.7.4.1: All Assessments – ASES Shoulder Score – Follow-up Visits to be compared

Evaluation Variable / Question	Level of Measurement	Coding and Analysis Plan
All Assessments - ASES Shoulder Score Within Subject Changes		
Creation of variable “ASES Total Score change between m and n [points]” Difference between “ASES Total Score m [points]” with “ASES Total Score n [points]” (Variable(s): FINSCORE)	Quantitative, interval	Calculate difference (could be negative or positive). Case summary with number and percentage of valid cases/values, missing cases/values (if any) and total cases/values. Mean, median, interquartile range, maximum, minimum, standard deviation, 95% confidence interval for mean, Shapiro-Wilk Test.

Table 6.7.4.2: All Assessments – ASES Shoulder Score Within Subject Changes

7. Table Templates (Tables, Figures, Listings - TFL)

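### SAP Table 6.7.1.2 chooses between paired t-test and Wilcoxon from the scores at each visit, not from the within-subject differences that Table 6.7.4.2 already tests for normality

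*SAP*

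**What the plan says.** SAP section 6.7.1 compares the total ASES score between every two visits from pre-operative to 120 months. For each pair, "either the parametric paired samples t-test or the non-parametric Wilcoxon test will be used", and the choice is made "Based on the underlying distribution of the data in both groups and the result of the normality assessment". The two variables named in Table 6.7.1.2 are the total scores at visit m and at visit n. The stated purpose is to evaluate change by subject. On status, the section says: "This analysis is part of the final report only".

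Three other places bear on the choice:

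- Section 3.1: "All quantitative variables will be assessed for normality using the Shapiro-Wilk test". This covers calculated variables too. No cut-off is given for the Shapiro-Wilk test itself.
- Section 4.10: "In case of deviation from assumptions (e.g. normality), non-parametric methods will be used for analysis". Transformation is ruled out.
- Section 6.7.4, Table 6.7.4.2, for the same kind of visit pairs: "Calculate difference (could be negative or positive"). It then lists the mean, median, SD, 95% confidence interval for the mean and a Shapiro-Wilk test of that difference. It does not say that this result decides the test in 6.7.1.

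**The concern.** A paired t-test is a one-sample t-test on the within-subject differences. Any normality assumption belongs to those differences; the distribution at either visit is irrelevant. The Wilcoxon signed-rank test, read as a test of location, also rests on the differences, through their symmetry. A difference is one variable, so data in both groups can only mean the two sets of visit scores.

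The mismatch matters most for a score with an upper limit. Post-operative scores that bunch near the maximum fail a normality test even where their differences from another visit look close to normal. The written rule, together with section 4.10, then sends the comparison to Wilcoxon for a reason unrelated to whether the t-test is valid. At stake is the match between the p-value in 6.7.1 and the mean change with its confidence interval in 6.7.4.

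**Working it through.** **Number of comparisons.** There are 13 visits (pre-operative, 6 weeks, 6 and 12 months, then yearly from 24 to 120 months). Pairs = 13 × 12 / 2 = 78.

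**The plan's own figures.** The documents give no power or error rate for these comparisons. The benchmark mean and SD in SAP Table 3.2 serve as inputs, and both reproduce as simple averages of the listed sources: 821.6 / 10 = 82.16, and 117.3 / 7 = 16.76. The only stated power, 80.3% for the primary test with n = 10, reproduces at 80.31% (two-sided one-sample t-test, 9 degrees of freedom, noncentrality √10 × 16.76/16.76 = 3.162). It has no bearing on section 6.7.1.

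**Distance to the ceiling.** Assume a maximum of 100. Then (100 − 82.16) / 16.76 = 1.06 SD. A normal score clipped to 0–100 and matched to mean 82.16 and SD 16.76 has about 24% of values at the ceiling. With SD 10.1, the lowest source SD, about 5% are there.

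**Simulation.** Correlated normal scores were clipped to 0–100, with 1,500 to 3,000 runs per scenario.

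- From the documents: mean 82.16; SD 16.76, or 10.1 as the low end; n = 100 (enrolment target) or 44, which is 100 × (1 − 0.56) after the planned drop-out.
- Assumed: the 0–100 range, pre-operative mean 35, between-visit correlation 0.3 to 0.95, Shapiro-Wilk cut-off 0.05.
- Written rule: t-test only if both visits pass. Difference-based rule: t-test if the paired difference passes.

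| Scenario | n | Both visits pass | Difference passes | Rules name different tests |
|---|---|---|---|---|
| Pre-op vs 24 months, SD 16.76, correlation 0.3–0.6 | 44 and 100 | 0–1% | 88–94% | 88–93% |
| Two post-op visits, SD 16.76, correlation 0.3–0.95 | 44 | 0–1% | 62–91% | 61–91% |
| Same | 100 | 0% | 21–86% | 21–86% |
| SD 10.1 post-op, correlation 0.3 (pre/post) or 0.6 (post/post) | 44 | 82–86% | 94–95% | 16–21% |
| Same | 100 | 44–58% | 94% | 42–55% |

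Further runs under somewhat different settings gave 0–3% for both visits passing at an SD near 17, and 14–25% disagreement at an SD of 10. Across all runs the disagreement is therefore about 14% to 93%.

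**What that does to the inference.**

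- No change, equal distributions, SD 16.76, n = 44 or 100: rejection 4.3–5.4% for the t-test and 4.3–5.3% for Wilcoxon.
- Mean moving from 77 to 82, correlation 0.6: power 54.9% (t) against 54.4% (Wilcoxon) at n = 44, and 90.3% against 89.3% at n = 100.
- Pre-operative against 24 months: 100% for both.
- The two selection rules lead to the same significance decision in 94–100% of samples. If the worst case applied to every pair, 0.06 × 78 = 4.7 decisions would differ.
- Equal means but unequal spread (SD 10.1 and 22.4): Wilcoxon rejects in 9.9% (n = 44) and 16.6% (n = 100), the t-test in 5.3% and 5.9%. Here the differences are skewed and pass Shapiro-Wilk in only 19% and 1% of runs, so a difference-based rule would mostly choose Wilcoxon as well.

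**The case against.** The case for leaving the text alone has four parts.

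1. The wording is not wholly closed. It adds the result of the normality assessment without naming a variable, section 3.1 applies Shapiro-Wilk to calculated variables, and Table 6.7.4.2 applies it to the differences. An analyst could look there. This stands in part: the SAP does plan the right check. But the text names the data in both groups and gives no cross-reference to 6.7.4, so the literal reading is the wrong one.
2. A reader might infer that the rule usually selects the wrong test. The documents do not support that. Wilcoxon is a valid paired test, and its error rate and power are nearly those of the t-test in most scenarios. The disagreement figures count which test is named, not which conclusion is reached. They also depend on a range, a ceiling and correlations that the documents do not give.
3. A reader might infer that the rule makes the test switch erratically between visit pairs. At an SD near 16.76 it hardly switches at all, because it nearly always gives Wilcoxon. A difference-based rule could switch more often.
4. A reader might infer that the mean change goes unreported when Wilcoxon is chosen. It does not: Table 6.7.4.2 gives the mean difference with its 95% confidence interval for every pair, whichever test is run. Only the accompanying p-value depends on the rule.

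Points 2 to 4 stand and limit the consequence. None of them makes the visit distributions the right basis for the choice.

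**Conclusion.** The criterion in Table 6.7.1.2 is wrong as written; the point is minor. The choice rests on the wrong quantity, while the right one is already computed and tested in 6.7.4 without a link. On the assumptions of a cap at 100, an SD near 16.76 and a Shapiro-Wilk cut-off of 0.05, the rule defaults to Wilcoxon for almost all comparisons involving a post-operative visit near the benchmark mean. With an SD near 10 the effect is weaker.

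The practical effect is that a p-value may not correspond to the mean change and interval beside it, and that a few of the 78 comparisons could change decision. The primary endpoint and the sample size are untouched.

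**What to change.** Amend Table 6.7.1.2 in one of two ways.

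- Minimum: state that the choice between the paired t-test and the Wilcoxon signed-rank test rests on the distribution of the within-subject difference defined in Table 6.7.4.2, and give the Shapiro-Wilk cut-off.
- Preferable: drop data-driven selection across the 78 pairs. Pre-specify the paired t-test to accompany the mean change and 95% confidence interval already in 6.7.4, with the Wilcoxon signed-rank test as a sensitivity analysis. Section 4.10 would then need a short exception for this table.

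The minimum change costs one sentence and uses output already planned. Its small downside is that the test may switch between visit pairs more often than now: in the post-operative runs at n = 100 the difference passed Shapiro-Wilk in anything from 21% to 86% of samples, depending on correlation. The preferable change avoids this and costs one further sentence in 4.10.

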6.7.2. Mortality

For analysis of the time to death or mortality, the Kaplan-Meier method will be used. The times between surgery and the most recent or last available assessment per subject will be used together with the times between surgery and the date of death. This analysis is part of the final report.

Evaluation Variable / Question	Level of Measurement	Recode and Analysis Plan
All Assessments – Mortality		
Creation of variable Difference between Date of Surgery [dd.mm.yyyy] and Date of Death [dd.mm.yyyy] in [days] (Variable(s): VISITDT; DOSEDD)		
	Quantitative, ratio	Case summary with number and percentage of valid cases/values, missing cases/values (if any) and total cases/values. Mean, median, interquartile range, maximum, minimum, standard deviation, 95% confidence interval for mean, Shapiro-Wilk Test.

Creation of variable Difference between Date of Surgery [dd.mm.yyyy] and Date of “most recent” Visit [dd.mm.yyyy] in [] days [] (Variable(s): VISITDT)	Quantitative, ratio	N/A (Analyzed above), used for survivorship
Create new variable “Grouping variable - Mortality” (Variable(s): PRIMRSN)	Qualitative, nominal	- censored = survivors - events = death
Create new variable “Combined Time - Mortality” (Variable(s): VISITDT; DOSEDD)	Quantitative, ratio	- Use time between surgery and most recent visit for surviving subjects - Use time between surgery and death for deceased subject
Use variables “Combined Time - Mortality” and “Grouping variable - Mortality”	Qualitative, nominal Quantitative, ratio	Case summary with number and percentage of valid cases/values, missing cases/values (if any) and total cases/values. Kaplan-Meier survival analysis: subject ID, time, status, cumulative proportion, Kaplan-Meier estimate, standard error of KM estimate, number of cumulative events, number of remaining cases, mean for survival time with 95% confidence interval, survival graph, hazard graph.

Table 6.7.2.1: All Assessments – Mortality Tables List

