This investigation is a prospective, multicenter clinical investigation. It is anticipated that a total of one hundred (100) subjects will be enrolled at approximately 4-7 sites. Neither subjects nor investigators are blinded to treatment and the clinical investigation does not include a contemporaneous control. The clinical investigation has been designed to follow the surgeon's standard of care for joint arthroplasty subjects, which entails clinical evaluation on a regular ongoing basis, or as needed should the subject become symptomatic in the treated joint. The enrollment period is expected to occur over 14 months.

8. Objective

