9.3. WITHDRAWAL CRITERIA

If during the clinical investigation a subject must be withdrawn prematurely, then the procedures outlined in this section must be followed. These procedures should not interfere with the initiation of any new treatments that are necessary to treat a subject's condition. Information on all withdrawn subjects will be documented.

Subjects may be withdrawn from the clinical investigation for any of the following reasons:

- i. Subject Withdrawal: A subject may voluntarily withdraw from the clinical investigation at any time and for any reason. The subject should be asked when possible, and without any form of coercion, the reason for his/her decision. If the participant withdraws from the clinical investigation completely, then data collected up until the point of withdrawal will be included in the final analysis.
- ii. Lost to Follow-Up (LTFU): A subject will be considered LTFU after all reasonable efforts have been made to contact the subject and request his/her continued participation in the clinical investigation. All attempts to contact the subject must be documented and should include at least two attempts to contact the subject by phone and one attempt via a certified letter. Data collected up until the point where the subject is LTFU will be included in the final analysis.
- iii. Removal of Device or AE/Incident: The discontinuation of a subject's participation in the clinical investigation due to the removal of the ReUnion TSA System or AE/incident that prohibits his/her continued participation must be fully explained. All available information concerning the removal of the device or AE/incident should be provided. Data collected up until the point of removal or AE/incident will be included in the final analysis.
- iv. Death: The discontinuation of a subject's participation in the clinical investigation due to death must be fully explained. All available information concerning the death or AE should be provided. Removal of a subject from continued follow-up in the clinical investigation due to death will not be considered a device failure unless the death is

directly caused by, or attributable to, the ReUnion TSA System. Data collected up until the point of death will be included in the final analysis.

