10.4. SCHEDULE OF EVENTS

Assessment	Pre-Operative	Operative/ Discharge	6 Weeks ^{a,b} (+/- 2 weeks)	6 Months ^{a,b} (+/- 3 weeks)	12 Months ^{a,b} (+/- 4 weeks)	24 Months ^{a,b} (+/- 4 weeks)	Annually ^b
Informed Consent	X						
Demographics & Medical History	X						

Inclusion/Exclusion	X						
Physical Exam	X		X ^c				
Surgical Procedure		X					
ASES Shoulder Score	X		X ^d				
Image Evaluation ^{e, f}	X	X	X	X	X	X	X
Subject Disposition ^g			X	X	X	X	X
	Device-Related AEs/Incidents & Reoperations will be collected throughout the course of the clinical investigation.						
	
 a. Follow-up visit schedule to reflect Institutions' Standard of Care practices b. If the subject misses a visit and is outside of the visit window, then every effort should be made to collect data instead of noting visit as missed. c. Evaluation may be collected when subject presents in-clinic for study visit. d. Evaluation can be collected via phone. e. Radiograph collection should follow Institution's Standard of Care practices and no additional x-rays should be made for study purposes. f. CT scans may be collected if part of Institution's Standard of Care practices. g. Subject Disposition assessment will occur at any time point for subject withdrawal prior to the completion of the clinical investigation. 						

Table 1: Schedule of Events

11. Statistical Methods

The 24 months post-operative results for subjects implanted with the ReUnion TSA System will be compared to a historical group and results reported by respective clinical outcome data in the scientific literature. The benchmark sources and values will serve as the control group for the ReUnion TSA System subjects.

Hypotheses are developed to allow for a comparison of 24 months post-operative ASES Shoulder Score results and 24 months effectiveness/performance between these two populations.

The Statistical Analysis Plan (SAP) lists all variables/questions within this clinical investigation. Therefore, no additional “evaluation” chapter is required nor needed for this CIP.

Data will be captured via IBM Clinical Development electronic data capture (EDC) system and statistical analysis will be performed using IBM SPSS. All statistical hypotheses tests will be with confidence levels (1- α) of 95% and power (1- β) of 80%. The significance level (α) is 0.05 and the beta-value (β) is set to 0.20. Therefore, p-values ≤ 0.05 will indicate statistical significance.

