6.6. ANALYSIS OF CI ENDPOINTS

Evaluation Variable / Question	Level of Measurement	Analysis Plan					
Endpoints – Primary Endpoint							

Use variable Total ASES Shoulder Score 24 Months [points]: Based on the underlying distribution of the data and the result of the normality assessment, either the parametric one-sample t-test or the non-parametric one-sample sign test will be used to compare the 24 months postoperative ASES Shoulder Score results of the ReUnion TSA group against the lower maximum acceptable difference ($-\theta$) of 65.40 points.
 
The analysis of the primary endpoint will be part of the final report.
							

Table 6.6.1: Endpoints – Primary Endpoint Tables List

Evaluation Variable / Question	Level of Measurement	Recode and Analysis Plan	Inclusion		
Adverse Events – Time to (earliest) Device-Related Adverse Event / Incident			IR	FR	N/A
Creation of variable Difference between Date of Surgery [dd.mm.yyyy] and Date of First Device Related Adverse Event [dd.mm.yyyy] in days / (Variable(s): VISITDT; AEONSTDT)	Quantitative, ratio	Case summary with number and percentage of valid cases/values, missing cases/values (if any) and total cases/values. Mean, median, interquartile range, maximum, minimum, standard deviation, 95% confidence interval for mean, Shapiro-Wilk Test.		X	
Creation of variable Difference between Date of Surgery [dd.mm.yyyy] and Date of “most recent” Visit [dd.mm.yyyy] in days / (Variable(s): VISITDT)	Quantitative, ratio	N/A (Analyzed above), used for survivorship		X	

Create new variable “Grouping variable – First Device Related Adverse Event” (Variable(s): AEONSTDT)	Qualitative, nominal	- censored = survivors - events = first (earliest) Device Related Adverse Event		X	
Create new variable “Combined Time – First Device Related Adverse Event” (Variable(s): AEONSTDT)	Quantitative, ratio	- Use time between surgery and “most recent” visit for surviving subjects - Use time between surgery and first device related adverse event for subjects with device related adverse event		X	

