6.7.3. Reoperation Surgery

For analysis of the time to the reoperation surgery, the Kaplan-Meier method will be used. The times between surgery and the most recent or last available assessment per subject will be used together with the times between surgery and the date of reoperation (earliest reoperation in case that one subject experienced more than one reoperation). This analysis is part of the final report.

Evaluation Variable / Question	Level of Measurement	Recode and Analysis Plan
Adverse Events / Reoperation Surgery		
Creation of variable Difference between Date of Surgery [dd.mm.yyyy] and Date of First Reoperation [dd.mm.yyyy] in [] days [] (Variable(s): VISITDT)	Quantitative, ratio	Case summary with number and percentage of valid cases/values, missing cases/values (if any) and total cases/values. Mean, median, interquartile range, maximum, minimum, standard deviation, 95% confidence interval for mean, Shapiro-Wilk Test.
Creation of variable Difference between Date of Surgery [dd.mm.yyyy] and Date of “most recent” Visit [dd.mm.yyyy] in [] days [] (Variable(s): VISITDT)	Quantitative, ratio	N/A (Analyzed above), used for survivorship
Create new variable “Grouping variable - First Reoperation” (Variable(s): VISITDT)	Qualitative, nominal	- censored = survivors - events = first (earliest) Reoperation
Create new variable “Combined Time - First Reoperation” (Variable(s): VISITDT)	Quantitative, ratio	- Use time between surgery and most recent visit for surviving subjects - Use time between surgery and first reoperation for subjects with reoperation(s)
Use variables “Combined Time - First Reoperation” and “Grouping variable - First Reoperation”	Qualitative, nominal Quantitative, ratio	Case summary with number and percentage of valid cases/values, missing cases/values (if any) and total cases/values. Kaplan-Meier survival analysis: subject ID, time, status, cumulative proportion, Kaplan-Meier estimate, standard error of KM estimate, number of cumulative events, number of remaining cases, mean for survival time with 95% confidence interval, survival graph, hazard graph.

Table 6.7.3.1: All Assessments – Reoperation Surgery Tables List

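### The SAP's Kaplan-Meier tables time events at their actual date but censor event-free subjects at their last visit, which biases estimated risk upward: modestly in the final report, possibly badly if curves are drawn annually

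*SAP*

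**What the plan says.** SAP 6.7.2 (Mortality) builds one time variable from two rules. For those who died: "Use time between surgery and death for deceased subject". For the others: "Use time between surgery and most recent visit for surviving subjects". SAP Table 6.6.2 does the same for the first device-related event: "Use time between surgery and first device related adverse event for subjects with device related adverse event", with event-free subjects again taken to their latest visit. SAP Table 6.7.3.1 repeats the construction for first reoperation. The only date variable the tables name for the censoring time is the visit date.

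Event capture is not tied to visits. The schedule of events (Protocol 10.4, SAP 4.4) states: "Device-Related AEs/Incidents & Reoperations will be collected throughout the course of the clinical investigation". For deaths, Protocol 9.3 says: "The discontinuation of a subject's participation in the clinical investigation due to death must be fully explained".

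Visits fall at 6 weeks, 6, 12 and 24 months and then yearly to 10 years. Both documents use an overall drop-out figure of 56%.

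On timing the documents differ. Protocol 11.3.3 and 11.3.4 put the secondary-endpoint and mortality analyses in the annual and final reports. SAP 3.1.2, 3.1.3, 6.7.2 and 6.7.3 say final report, and Table 6.6.2 ticks only the final-report column.

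**The concern.** Kaplan-Meier estimation needs follow-up to end for each subject at a time that does not depend on whether the event happened. Here it does depend on it. A subject with an event is kept at risk to the event date, up to a year or so beyond the last visit. A subject without one is removed at the last visit, even when known to be alive and unrevised later. Every death necessarily falls after that subject's last visit, so for mortality the asymmetry touches every event.

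In the final report a subject who stays to the end is censored at the 120-month visit, and earlier gaps between visits do no harm because a later visit covers them. The bias comes from those who leave early. At an annual data cut, everyone still in the study has an open gap since the last visit, so the problem is general.

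Device-related events are a named secondary safety endpoint, and time to reoperation is the SAP's nearest output to implant survivorship. The SAP also asks for mean survival time and a survival graph, both sensitive to the tail.

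**Working it through.** The documents give no figure for these curves, so there is none to reproduce. Event rates, the shape of drop-out and the reading of 56% as loss by 10 years are assumptions.

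**Mechanism by hand.** At each event the survival estimate is multiplied by 1 − 1/n, where n is the number at risk. Take 100 subjects, 99 event-free and last seen at 24 months, and one death at 30 months.
- SAP rule: the 99 left at 24 months, so n = 1 and survival = 1 − 1/1 = 0%.
- The 99 known alive at 33 months: n = 100 and survival = 1 − 1/100 = 99%.

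**Final report.** Inputs from the documents: N = 100, the visit schedule and 56% drop-out. Assumed: exponential drop-out at rate −ln(1 − 0.56)/10 = 0.082 per year, and constant event hazard h, so that true 10-year risk = 1 − exp(−10h). Mean estimated 10-year risk over 4,000 simulated data sets:

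| h per year | True | Events captured to drop-out: SAP rule / symmetric | Events captured to next scheduled contact: SAP rule / symmetric |
|---|---|---|---|
| 0.5% | 4.88% | 5.16% / 4.97% | 5.35% / 4.96% |
| 1% | 9.52% | 9.82% / 9.47% | 10.19% / 9.48% |
| 2% | 18.13% | 18.69% / 18.05% | 19.35% / 18.05% |
| 3% | 25.92% | 26.78% / 25.92% | 27.66% / 25.92% |

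The excess over symmetric censoring runs from 5.16 − 4.97 = 0.2 to 27.66 − 25.92 = 1.7 percentage points, or about 3% (26.78/25.92) to 8% (5.35/4.96) in relative terms. With 20% drop-out it is about 1 to 2%. It vanishes if no event after a leaver's last visit is ever recorded (18.06% against a true 18.13% at h = 2%).

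Scaled to a true risk of exactly 10%, the SAP rule gives about 10.3% and 10.8% in the two capture cases, against 9.9% to 10.1% with symmetric censoring. The sampling SD of the estimate is about 4 points.

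**Annual report, if drawn.** Inputs: 100 subjects, 14-month accrual and visits varying by ±4 weeks. Assumed: no drop-out, true 10-year risk 10%, and cuts 3.0 to 3.6 years after first surgery. The true risk at the cut is about 3.1% to 3.7%. Under the SAP rule the mean estimate is about 7% to 18% depending on the cut, the median stays near the truth, and the curve reaches 0% survival in about 1% to 11% of data sets.

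These figures are fragile. At the 3.0-year cut, collapse occurs in about 6% of data sets with visit variation and about 36% with visits exactly on schedule. With on-schedule visits, 56% drop-out, hazards of 1% to 3% per year and cuts at 3 to 6 years, collapse ranges from 23% to 62%. At the higher hazards the median also moves (9.7% against a true 5.8% at 2% per year, 3-year cut).

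**The case against.** Four points deserve weight.

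- **Late events.** A reader might infer that events are counted however long after a subject has left. If half or all of them were learned of, a true 10% would be estimated at about 12.8% or 15.2%. The documents do not support that. Protocol 9.3 brings in data up to the point of withdrawal, loss, removal or death, and no process is described for learning of events afterwards. This stands, and those figures should not be used.
- **Annual collapse.** It depends on the Protocol's placement of these curves. The SAP puts them in the final report, and its revision history records a change to separate interim from final analyses. This also stands: the collapse is conditional.
- **Visit pattern.** A reader might infer from Protocol section 7 that subjects return only when symptomatic. It provides for regular evaluation, "or as needed should the subject become symptomatic in the treated joint", so symptoms are an additional reason to be seen. Protocol 10.3 sets scheduled visits with a site contact beforehand.
- **Phone contacts.** The SAP narrative in 6.7.2 and 6.7.3 also allows the last available assessment, and the ASES score may be taken by phone. If such contacts count, the gap shrinks. But the tables say visit, name only the visit date, and provide phone collection for ASES alone.

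Finally, the final-report bias is about 0.1 to 0.2 of a sampling SD, errs towards overstating harm, and no test or stopping rule hangs on these curves. That limits the consequence. It does not make the rule correct.

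**Conclusion.** The rule as written is asymmetric in all three tables and biases estimated risk upward whenever an event after a subject's last visit is recorded. In the final report the size is modest: about 0.3 to 0.8 points on a true 10-year risk of 10%, given a constant hazard and 56% exponential drop-out by 10 years. Whether it arises at all depends on events being captured between the last visit and exit, which the continuous collection of events and the recording of death as an exit reason make likely. In annual reports the tail could be seriously misleading, but only if the Protocol's timing prevails, and the size there varies so much with cut date, hazard and visit timing that no single figure should be relied on. The change is worth making because it is cheap and these are the 10-year safety outputs.

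**What to change.** In SAP Tables 6.6.2, 6.7.2.1 and 6.7.3.1, define one end-of-follow-up date per subject that does not depend on whether the event occurred:

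1. the report cut-off or 10-year date, where status is confirmed to that date;
2. otherwise the study-exit (disposition) date for withdrawn or lost subjects, if status was established then;
3. otherwise the last documented contact at which event status was established.

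Censor event-free subjects at that date, count events, including deaths, on or before it, and list later-learned events separately. For mortality, censor survivors at the last date known alive within that window and count deaths during active follow-up. Deaths must not be truncated at the deceased subject's own last-known-alive date, since that would exclude every death.

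State whether a phone contact counts as a last available assessment, and reconcile Protocol 11.3.3 and 11.3.4 with the SAP on whether these curves appear in annual reports.

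Cost: SAP wording plus a status date recorded at each contact. Protocol 9.3 already requires documentation of contact attempts for lost subjects, which "should include at least two attempts to contact the subject by phone and one attempt via a certified letter", but not of event status when contact is made, so a small data-collection addition is needed. A few late-learned events move from the curve to a listing.
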